## 4.2 SCIENTIFIC RATIONALE FOR STUDY DESIGN

In each of the Studies A, B, and C, a randomized, placebo-controlled study design where the effect of the IMP is assessed in CSU patients with moderate to severe symptoms on top of optimized background therapy is considered to be the most appropriate design to explore the efficacy and safety of dupilumab in participants with CSU who remain symptomatic despite the use of H1-AH and who are omalizumab naïve or intolerant or incomplete responders.

Study A and Study C will target omalizumab naïve patients; more than 50% of CSU patients do not respond to H1 antihistamine treatment ([1, 9](#)). In Study A, overall 52% of participants received H1-AH at recommended doses as background therapy and 45% of participants presented with angioedema at baseline. In order to maintain consistency between the study population in studies A and C, and reflect the real-life distribution of patients with angioedema and uncontrolled by both standard dose or maximal H1-AH therapy, it is planned that Study C would include not more than approximately 50% (n=75) of participants having their H1-AH therapy at recommended doses (for more details please see [Section 6.1.2](#)), and not less than approximately 30% (n=45) but not more than approximately 45% (n=68) of participants presenting with angioedema at baseline.

As mentioned in [Section 2.1](#), dupilumab at SC doses of 300 mg and 200 mg have been observed to suppress both total and antigen specific IgE levels across the indications studied: AD, asthma, and CRSwNP.

Study B will target omalizumab treated CSU patients. Approximately 20% to 40% patients don't respond to omalizumab and remain without an effective third-line treatment; these patients have the highest unmet medical need ([1](#)). Studies suggests that omalizumab incomplete or

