### Methods of assigning patients to treatment group

The randomized intervention kit number list is generated centrally by Sanofi and IMPs (dupilumab 300 mg, dupilumab 200 mg, or their matching placebo) are packaged in accordance with this list. The randomization and intervention allocation are performed centrally by an IRT. The IRT generates the participant randomization list and allocates the intervention number and the corresponding intervention kits to the participants according to it.

Participants will be randomized in a 1:1 ratio treatment arm described in [Table 3](#).

The randomization will be stratified first by age (adults versus adolescents versus children in Study A and Study C and adults versus adolescents in Study B; up to approximately 5% of total sample size for children and approximately 5% of total sample size for adolescents in Study A and Study C; up to approximately 5% of total sample size for adolescents in Study B). In adults, randomization will be stratified further by country (Study A, B and C) and presence of angioedema at baseline (Study C only). In adolescents/children  $\geq 6$  to  $< 12$  years of age, randomization will not be stratified further. In Study A, overall 52% of participants received H1-AH at recommended doses as background therapy, and 45% of participants presented with angioedema at baseline. To maintain consistency between the study population in studies A and C, and reflect the real-life distribution of patients with angioedema and uncontrolled by both standard dose or maximal H1-AH therapy, it is planned that Study C would include not more than

approximately 50% (n=75) of participants having their H1-AH therapy at recommended doses (for more details please see Section 6.1.2), and not less than approximately 30% (n=45) but not more than approximately 45% (n=68) of participants presenting with angioedema at baseline.

It is anticipated that approximately 30%-40% of enrolled participants will have angioedema.

A randomized participant is defined as a participant who has been allocated to a randomized intervention regardless whether the treatment was administered or not (ie, participant registered by the IRT). A participant cannot be randomized more than once in the study.

Investigational medicinal products will be dispensed at the study visits summarized in the Schedule of activities (SoA).

Returned IMP should not be re-dispensed to the participants.

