#### **6.5.1 Rescue medicine**

All participants on 1- to 3-fold the approved non-sedating H1-AH dose (maintenance dose used at screening) will be allowed to take additional doses of their H1-AH medications as rescue therapy as long as they do not exceed 4-fold the recommended dose during the screening, treatment, and follow-up periods. If symptoms are still uncontrolled after increase of H1-AH to the maximum allowed dose, participants can take a short course of OCS as rescue therapy during the treatment and follow-up periods. The participants on stable dose of 4-fold the approved H1-AH dose will be allowed to take a short course of OCS as rescue therapy during the treatment and follow-up periods. In order to ensure consistency, when possible, it is recommended to use OCS for 5 to 7 days with a starting dose of oral prednisone 40 mg (or clinically comparable OCS) followed by taper per the Investigator's judgment.

For rescue medication in participants in Japan, please see Appendix 11 ([Section 10.11](#)).

The initial maintenance antihistamine dose should remain stable throughout the study, and participants should continue their maintenance dose once rescue treatment is no longer required.

The use of permitted rescue medications should be delayed, if possible, for at least 8 weeks following the initiation of the investigational treatment. The date and time of rescue medication administration as well as the name and dosage regimen of the rescue medication must be recorded.

For other information related to H1-AH and OCS including safety precautions please refer to the National Product labeling.

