At the Study B interim analysis, it is estimated that 40 participants per group will provide 74% power to detect a treatment effect of 5 or higher with SD 7 and minimal detectable difference (MDD) of approximately 3.8 for ISS7 and a treatment effect of 10 or higher with SD 14 and MDD of approximately 7.6 for UAS7 between the dupilumab arm and placebo using a 2-sided t-test with alpha = 0.021.

With the decision process outlined in [Section 9.5](#), the overall power for the study will be approximately 88%.

**For Study C (omalizumab naïve):** Assumptions for sample size calculations for Study C were made by considering Study A results. An effect size of 0.564 or higher is assumed. Based upon an SD of 7.5 (pooled SD from the observed data in Study A), a treatment difference of 4.23 in the ISS7 would correspond to an effect size of approximately 0.564. Based upon an SD of 14.3 (pooled SD from the observed data in Study A), a treatment difference of 8.53 in the UAS7 would correspond to an effect size of approximately 0.597. Based on this assumption, plus the assumption of a 10% dropout rate, it is estimated that 75 participants per group will provide 90% power to detect an effect size of 0.564 or higher between the dupilumab arm and placebo using a 2-sided t-test with alpha = 0.05. This sample size estimate applies to both ISS7 (primary endpoint for all countries except EU and EU reference countries) and UAS7 (primary endpoint for EU and EU reference countries).

The sample size calculations and the alpha spending by O'Brien-Fleming approach were calculated by nQuery Advisor and nTerim 4.0.

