The primary efficacy endpoints will be analyzed using an analysis of covariance (ANCOVA) model with the baseline value of the primary endpoint, intervention group, presence of angioedema at baseline, and region as covariates, with intercurrent events and missing data being handled by a hybrid method of the worst-observation carried forward (WOCF) and multiple imputation. For participants taking selected prohibited medications and/or rescue medications (see [Table 4](#)), their data after the medication start date will be excluded, and the worst postbaseline value on or before the time of the medication usage will be assigned to the Week 24 value (for participants whose postbaseline values are all missing, the baseline will be used). Participants who discontinue the intervention prematurely are encouraged to follow the planned clinical visits and in these participants who did not take the selected prohibited medications and/or rescue medications, all data collected after intervention discontinuation will be used in the analysis. For these participants, missing data may still happen despite all efforts to collect the data after intervention discontinuation. For participants who discontinue study intervention due to lack of efficacy, all data collected after discontinuation will be used in the analysis, and a WOCF approach will be used to impute missing Week 24 value if needed (ie due to study discontinuation). For participants who discontinued study intervention for reasons other than lack of efficacy, a multiple imputation approach will be used to impute the missing Week 24 value. This multiple imputation will include all participants except participants who have taken the selected prohibited medications and/or rescue medications on or before Week 24 and will also exclude participants who discontinued study intervention due to lack of efficacy on or before Week 24.

Each of the imputed complete data will be analyzed by fitting an ANCOVA model as described above. Statistical inference obtained from all imputed data will be combined using Rubin's rule. Descriptive statistics including number of participants, mean, standard error, and least squares (LS) mean changes (and standard error) score will be provided. In addition, difference of the dupilumab group against placebo in LS means and the corresponding 95% confidence intervals (CI) will be provided along with the p-values.

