4.3.5 Subgroup analyses

To assess the homogeneity of the treatment effect across various subgroups, analyses will be performed on the primary endpoint (ISS7 and UAS7) across the following subgroups:

- Age group (<median, \geq median; <65 , ≥65 years)
- Gender (Male, Female)
- Baseline weight (<median, \geq median, <60 , ≥60 kg)
- Baseline BMI (<25 , ≥25 - <30 , ≥30 kg/m²)
- Region (see [Section 5.3](#))
- Territory (see [Section 5.3](#))
- Race (White, all the Others)
- Ethnicity (Hispanic, non-Hispanic)
- Angioedema at baseline (Yes, No)
- Baseline UAS7 score (<28 , ≥28)
- Baseline ISS7 score (<13 , ≥13)
- Duration of disease (<2 , 2-10, >10 years)
- H1-AH baseline dose (1-fold, 2-4-fold)
- Baseline Total serum IgE (<100 IU/mL, ≥100 IU/mL)

To assess the consistency of the treatment effects across the subgroup levels, subgroup analyses will be conducted for the primary endpoint at Week 24. The analysis will be performed based on imputed datasets from the primary analysis.

To test the interaction between intervention and subgroup factor, an ANCOVA model incorporating subgroup-by-treatment interaction will be built for each subgroup factor. The model will include all the covariates in the main statistical model plus the subgroup variable (if not one of the covariates adjusted in the main model already) and the subgroup-by-treatment interaction. Statistical inference obtained from all imputed data will be combined using Rubin's rule. A p-value for the test of interaction will be provided based on the combined inference.

In each subgroup, the primary endpoint will be analyzed using the primary approach for the primary endpoint, but on the specific subgroup of the imputed primary analysis population. Descriptive statistics including number of participants, mean, standard error, and least squares (LS) means for each subgroup will be provided. In addition, difference in LS means and the corresponding 95% confidence intervals (CI) will be provided for each subgroup. Forest plots will be provided.

In addition, the primary endpoint will be analyzed in the subgroups of adults and adolescent participants.

China subpopulation will be considered for primary efficacy, key secondary efficacy, and important safety analyses (which are for China submission and may be performed outside of the main Clinical Study Report).

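### Study C caps enrolment on baseline H1-AH dose, which influences the first rescue step, but omits it from the strata, the primary ANCOVA and the imputation model: validity is intact, a little precision is lost

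*Protocol*

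**What the plan says.** **Enrolment.** Protocol 4.2 (also the Synopsis and 6.3) names two features to keep Study C comparable with Study A: H1-AH dose and angioedema. Both have enrolment limits. For dose, "it is planned that Study C would include not more than approximately 50% (n=75) of participants having their H1-AH therapy at recommended doses".

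**Randomisation.** After age, Protocol 6.3 states: "In adults, randomization will be stratified further by country (Study A, B and C) and presence of angioedema at baseline (Study C only". Dose is not listed.

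**Primary model.** Study C SAP 4.3.2 specifies an ANCOVA "model with the baseline value of the primary endpoint, intervention group, presence of angioedema at baseline, and region as covariates". The imputation regression step in SAP Appendix 5 adjusts for treatment, region, angioedema and baseline score. Dose is in neither.

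**Rescue.** Under Protocol 6.5.1, participants on 1- to 3-fold background may first take extra H1-AH up to 4-fold, and then OCS if still uncontrolled. For those already at the ceiling: "The participants on stable dose of 4-fold the approved H1-AH dose will be allowed to take a short course of OCS as rescue therapy". In Japan the ceiling is 2-fold (Protocol Appendix 11).

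**Handling in the analysis.** In Study C SAP Table 4, extra H1-AH is marked No, so Week 24 data are kept. Systemic corticosteroids are marked Yes. If blinded medical review confirms use for CSU treatment failure, the worst post-baseline value up to that point is assigned to Week 24.

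**Where dose is used.** SAP Appendix 3 tabulates it by arm as 1-fold, 2-3-fold and 4-fold. SAP 4.3.5 has a subgroup and interaction analysis by "H1-AH baseline dose (1-fold, 2-4-fold".

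**The concern.** Two baseline features are singled out for control, but only one is carried through. Angioedema is capped, stratified in adults, and included in the ANCOVA and the imputation. Dose is capped and then left out, and no reason is given.

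Dose is a plausible predictor of the primary outcome under the plan's own rules. A participant at the H1-AH ceiling has no antihistamine step left before OCS, and confirmed OCS use replaces the Week 24 score. If dose is prognostic, an unstratified and unadjusted dose factor leaves two things in the estimate: whatever between-arm imbalance arises by chance, and a share of outcome variance that a covariate would remove. If the sponsor sees an imbalance only after unblinding, any adjustment will be post hoc.

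**Working it through.** **Inputs from Protocol 9.2.** "Based upon an SD of 7.5 (pooled SD from the observed data in Study A), a treatment difference of 4.23 in the ISS7"; "plus the assumption of a 10% dropout rate, it is estimated that 75 participants per group will provide 90% power"; "using a 2-sided t-test with alpha = 0.05". Allocation is 1:1.

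**Inputs assumed.** The documents give no prognostic effect of dose on ISS7 change (b) and no share at the H1-AH ceiling. I take b = 1, 2 or 3 points. For the share q I use 0.50 (the level of the cap at the recommended dose) and 0.25 or 0.10 (possible shares at the ceiling).

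**Step 1: reproduce the plan.** Effect size 4.23/7.5 = 0.564. Normal approximation: n = 2(1.960 + 1.282)²/0.564² = 66.1, so 67 per arm; 67/0.9 = 74.4, so 75. The exact t calculation gives 68, inflated to 76. With 75 × 0.9 = 67.5 evaluable per arm, noncentral-t power is 0.902. The stated design reproduces.

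**Step 2: chance imbalance.** SD of the between-arm difference in share = √(2q(1−q)/75). At q = 0.50 this is √(0.5/75) = 0.0816, so the 95% range is ±1.96 × 0.0816 = ±0.160, or 16 percentage points.

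**Step 3: shift in the ISS7 difference.** Shift = b × imbalance; 95% range:

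| Share q | b = 1 | b = 2 | b = 3 |
|---|---|---|---|
| 0.50 | ±0.16 | ±0.32 | ±0.48 |
| 0.25 | ±0.14 | ±0.28 | ±0.42 |
| 0.10 | ±0.10 | ±0.19 | ±0.29 |

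At q = 0.50 these are 4%, 8% and 11% of 4.23. Against a standard error of 7.5 × √(2/67.5) = 1.29, they are 0.12, 0.25 and 0.37 SE.

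**Step 4: precision gained by adjusting (q = 0.50).** R² = b² × 0.25/7.5² = 0.4%, 1.8% and 4.0%. The SE is multiplied by √(1−R²), a fall of 0.2%, 0.9% and 2.0%. Power rises from 0.902 to 0.903, 0.907 and 0.913.

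**Step 5: validity.** I simulated the comparison with and without a two-level dose covariate (10,000 runs, 68 per arm, q = 0.50, b = 1 and 3). With no treatment effect, rejection rates were 0.051 without the covariate and 0.050 with it. With a true difference of 4.23, the mean estimate was 4.25 (b = 1) or 4.22 (b = 3) in size under both models.

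These figures treat dose as unrelated to country, region, angioedema and baseline score. Any correlation with those would leave less to remove.

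**The case against.** The strongest reply is that this is a choice among covariates and not a defect. Chance imbalance is random error that the unadjusted SE already covers, and the same could be said of any omitted baseline variable. The cap is justified by consistency with Study A and real-life case mix, not by a claim that dose predicts outcome. All of this stands, and it limits the point to precision and robustness.

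A reader might infer that dose decides whether Week 24 is observed or replaced. The documents do not support that. Participants on 1- to 3-fold can also reach OCS, some at any dose may need no rescue, and replacement requires blinded confirmation. Dose can change only the likelihood.

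A reader might also take the capped variable to be the one that switches the rescue route. It is not. The cap cuts at the recommended dose, whereas direct OCS applies at 4-fold (2-fold in Japan). A covariate in the subgroup categories, 1-fold against 2-4-fold, would pool participants on 2- to 3-fold, who outside Japan share the 1-fold rescue ladder, with those at the ceiling.

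The plan also has related provisions. The baseline table would show an imbalance, and the subgroup model contains dose. In SAP 4.3.4, the as-observed analysis keeps post-rescue data and the worst-possible-score analysis stresses the opposite assumption. None of these specifies an overall treatment estimate adjusted for dose, so the gap remains.

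Finally, the change is not free. The protocol itself lists the covariates (Synopsis; 9.4.1, Table 7), and Study A used the same model. Both costs are real but small.

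**Conclusion.** The point holds as a minor one. Study C controls enrolment on baseline H1-AH dose and lets it influence the first rescue step, but does not use it in stratification, the primary ANCOVA or the imputation. At a 50% share, the conditional 95% chance shift is about ±0.16 to ±0.48 ISS7 points, and the power forgone is about 0.1 to 1.1 percentage points. These sizes rest entirely on the assumed prognostic effect of 1 to 3 points; if dose is not prognostic, there is nothing to recover. At shares of 10–25% the shifts are smaller.

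It would be wrong to infer that the primary analysis is biased or its error rate inflated. Randomisation protects both, and the simulation agrees. The stated sample size and power also stand. The case for acting is that dose is already recorded and categorised, so a pre-specified adjustment costs almost nothing.

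**What to change.** Before unblinding, add baseline H1-AH dose to the Study C ANCOVA for ISS7 and UAS7 (SAP 4.3.2 and Table 2) and to the imputation regression step (SAP Appendix 5), so that the two models agree. Code it in one of two ways:

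- **The three levels in SAP Appendix 3** (1-fold, 2-3-fold, 4-fold; 2 df). These cover the enrolment cap and, outside Japan, the rescue cut.
- **At the locally allowed maximum versus below** (1 df). This covers the rescue cut everywhere, including the 2-fold ceiling in Japan.

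Keep the current model, which matches Study A, as a sensitivity analysis. If the sponsor prefers to leave the primary model alone, the minimum is to pre-specify the dose-adjusted ANCOVA as the sensitivity analysis.

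The cost is 1–2 degrees of freedom, SAP wording, a matching edit to the protocol covariate list if the primary model changes, and a small departure from Study A's model. No new data are needed.

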#### **4.3 JUSTIFICATION FOR DOSE**

Based on the known pharmacokinetics (PK), safety and efficacy of dupilumab, the selected dosing regimen is dupilumab 300 mg q2w with a loading dose of 600 mg for adults; and 300 mg q2w with a loading dose of 600 mg for adolescents  $\geq 60$  kg OR 200 mg q2w with a loading dose of 400 mg for adolescents  $<60$  kg. These are the approved dose regimens for AD, another skin disease. The doses proposed for children  $\geq 6$  to  $<12$  years of age are the dose regimens for the same age for AD, which have been submitted to the Health Authorities and are currently in review: 200 mg q2w with a loading dose of 400 mg for children  $\geq 6$  to  $<12$  years of age with weight  $\geq 30$  kg or 300 mg q4w with a loading dose of 600 mg for children  $\geq 6$  to  $<12$  years of age with weight  $<30$  kg and  $\geq 15$  kg. The proposed doses are expected to achieve concentrations in serum that saturate the IL4/13 receptor in most patients and hence they are expected to provide the maximum benefit and therefore to achieve the optimal benefit/risk ratio in this patient population. Organ perfusion is anticipated to be similar between AD and CSU and lower than the rate of lung perfusion.

Furthermore, for AD a loading dose was administered to more rapidly achieve effective drug concentrations, thereby allowing a rapid pharmacodynamics (PD) response as demonstrated by improvement in pruritus, a hallmark of AD. Similarly, as pruritus is a core symptom of CSU, and to achieve effective drug concentrations more rapidly, a loading dose is selected for this study.

EFC16461 Study A (n=138) conducted in adults, adolescents and children ages 6-11 years with CSU who remain symptomatic despite the use of H1 antihistamine (H1-AH) treatment demonstrated that dupilumab at dose regimens described above provide clinically meaningful and statistically significant improvement versus placebo, across the key symptoms of CSU (including itch, hives and overall urticaria activity) at Week 24 and is well tolerated in the studies population.

#### **4.4 END OF STUDY DEFINITION**

A participant is considered to have completed the study if he/she has completed all phases of the study including the last end of study (EOS) Visit. If a participant discontinues treatment period prematurely but completes follow-up to the planned EOS Visit, he/she is considered a completer.

The overall EOS is defined as the date of the last visit of the last participant in the study.

## 5 STUDY POPULATION

Prospective approval of protocol deviations to recruitment and enrollment criteria, also known as protocol waivers or exemptions, is not permitted.

### 5.1 INCLUSION CRITERIA

For each of the 3 Studies A, B, and C, participants are eligible to be included in the study only if all of the following criteria apply:

#### Age

I 01. Study A and C: Participant must be  $\geq 6$  years to 80 years of age at the time of signing the informed consent.

Study B: Participant must be  $\geq 12$  years (or the minimum legal age for adolescents in the country of the investigational site) to 80 years of age at the time of signing the informed consent

Note: For those countries where local regulations do not permit enrollment of children aged  $\geq 6$  to  $<12$  years, the recruitment will be restricted to those who are  $\geq 12$  years of age (or the minimum legal age for adolescents in the country of the investigational site). For those countries where local regulations do not permit enrollment of children aged  $\geq 6$  to  $<12$  years of age and adolescents, the recruitment will be restricted to those who are  $\geq 18$  years of age. See instructions specific to France in Appendix 11 ([Section 10.11.2](#)).

